### **Action to Be Taken by Investigator:**

If any one of abnormal liver chemistry criteria is met, the investigator or sub-investigator must do the following:

- Following the initial observed elevation, every effort should be made to have the patient reassessed within 48 to 72 hours to repeat liver function chemistries and for further hepatic evaluation.
- Patients must be monitored 2 to 3 times per week until liver function chemistries (ALT, AST, ALP, total bilirubin) resolve, stabilize or return to within the normal range or to baseline levels.
- This event must be reported to the sponsor within 48 to 72 hours of learning after its occurrence on the Liver Event Form.
- Consultation with a specialist such as a hepatologist is considered.
- Liver imaging (ie, ultrasound, magnetic resonance imaging [MRI], computerized tomography (CT) is considered.

- For criteria c, termed “Hy’s law,” the case must be reported as an SAE (if baseline AST or ALT is  $\leq$  ULN).  
If baseline AST or ALT is  $>$  ULN, the case that meets the following criteria must be reported as an SAE.  
AST or ALT  $>$  3  $\times$  increase from baseline AST or ALT and TBL  $>$  2  $\times$  increase from baseline TBL

### **Follow-up Examination:**

If any of abnormal liver chemistry criteria are met, the following assessments should be obtained at FUP and documented in the Liver Event Form:

- Clinical signs and symptoms course
- Concomitant medications: OTC/herbal/dietary supplements (start and stop dates)
- Alcohol use
- Risk factors for nonalcoholic steatohepatitis (NASH) such as diabetes, obesity and hypertriglyceridemia
- Autoimmune hepatitis/cholangitis
- Wilson's disease
- Laboratory Assessments
  - Viral hepatitis serology
    - Hepatitis A IgM antibody
    - Hepatitis B surface antigen and Hepatitis B core antibody (IgM)
    - Hepatitis C RNA
    - Hepatitis E IgM antibody
    - Cytomegalovirus IgM antibody
    - Epstein-Barr viral capsid antigen IgM antibody

For patients with total bilirubin of  $>$  1.5 ULN, conjugated bilirubin should be measured

Complete blood count with differential

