### 2.2 Secondary Objectives

- To assess the safety of S-649266

The other secondary objectives of this study are established as follows:

- To assess the clinical outcome of treatment with S-649266 or BAT in patients with either HAP/VAP/HCAP or BSI/sepsis at End of Treatment (EOT) and Follow-up (FUP)
- To assess the clinical outcome of treatment with S-649266 or BAT in patients with cUTI at EOT, TOC, and FUP
- To assess the microbiologic outcome of treatment with S-649266 or BAT in patients with either HAP/VAP/HCAP or BSI/sepsis at EOT, TOC, and FUP
- To assess the microbiologic outcome of treatment with S-649266 or BAT in patients with cUTI at EOT and FUP
- To assess the microbiologic outcome of treatment with S-649266 or BAT in patients with bacteremia (regardless of the primary infection diagnosis) at EOT, TOC, and FUP
- To assess the composite clinical and microbiologic outcome of treatment with S-649266 or BAT in patients with cUTI at EOT, TOC, and FUP
- To assess the all-cause mortality at Day 14 and Day 28 in patients with HAP/VAP/HCAP and BSI/sepsis
- To assess the relationship between the PD parameter %fT>MIC based on plasma drug concentrations at steady state and the clinical and microbiologic outcomes of treatment with S-649266 in patients with HAP/VAP/HCAP, cUTI, or BSI/sepsis

---

 TOC is defined as end of treatment (EOT) + 7 days (± 2 days).

 BSI/sepsis is a group of patients with documented carbapenem-resistant Gram-negative infections in the blood stream (BSI) or in a body site other than the urinary tract (cUTI) or lung (HAP/VAP/HCAP) and in case of sepsis, evidence of systemic inflammatory response syndrome (SIRS) is required.

 EOT = end of treatment is defined as the last day of study therapy.

 FUP = follow-up is defined as EOT + 14 days (± 3 days).

- To assess the resource utilization required for the treatment of the study-qualifying infection
- To compare S-649266 with BAT in patients with HAP/VAP/HCAP, cUTI, or BSI/sepsis based on the composite endpoint of survival and no change in antibiotic treatment due to either lack of therapeutic benefit or drug-related toxicity at TOC

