**Table 7-1 Clinical Laboratory Tests**

Category	Evaluation Items
Hematology Tests	Hematocrit, Hemoglobin, Platelet count, RBC count, WBC count with differential and morphology indices INR and PTT
Blood Chemistry Tests	ALP, ALT, AST, GGT, LDH, CPK, CRP, and Amylase BUN, Creatinine, TBL Sodium (Na), Potassium (K), Bicarbonate (HCO 3 ), Chloride (Cl), Calcium (Ca), Magnesium (Mg) Glucose, Total protein, Albumin, Uric acid, Total cholesterol
Urinalysis	Glucose, Blood, Protein, Ketones, Bilirubin, Urobilinogen, Leukocyte esterase, Microscopic a (WBC, RBC, Crystal and casts)
Specialized Tests	Iron, TIBC, Transferrin iron saturation, and Hepcidin at Screening and TOC
Others	Serum or urine pregnancy: at Screening CrCl and eGFR at Screening and EA CrCl determined from a timed urine collection at EA b

RBC = red blood cell; WBC = white blood cell; INR = international normalized ratio; PTT = partial thromboplastin time; ALP = alkaline phosphatase; ALT = alanine aminotransferase; AST = aspartate aminotransferase; GGT = gamma glutamyl transferase; LDH = lactate dehydrogenase; CPK = creatine phosphokinase; CRP = C-reactive protein; BUN = blood urea nitrogen; TBL = total bilirubin; TIBC = total iron-binding capacity; TOC = test of cure; CrCl = creatinine clearance; eGFR = estimated glomerular filtration rate; EA = early assessment

a If sediment is present

b For patient with eGFR  $\geq$  90 mL/min/1.73 m^2 at Screening

Blood and urine samples for clinical laboratory tests will be collected at specified times. Blood samples for all clinical laboratory tests will be collected in the fasted state, if possible.

The samples other than some specialized tests will be measured at a local laboratory and results will be entered in the eCRF. The samples for serum iron, TIBC, transferrin iron saturation, and hepcidin will be shipped to a central laboratory. Details procedures for sample collection, handling, labeling, storage, and shipping will be provided in the separate study procedure manual. Shipping labels, instructions for shipping and courier service will be provided from the sponsor or CRO.

The investigator or sub-investigator will assess whether any abnormal changes from baseline are clinically significant (See also Section 7.12.6).

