#### **7.12.6.1 Liver Abnormalities**

Management and Discontinuation Criteria for Abnormal Liver Function tests have been designed to ensure patient safety and evaluate liver event etiology. The investigator or sub-investigator must review study patient laboratory results as they become available to identify if any values meet the criteria in Appendix 9. When any test result meets the management criteria for liver function abnormalities, the results of further assessments and required follow-up should be recorded in the Liver Event Form.

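### Appendix 9 names viral hepatitis serology and part of the etiology history only at FUP, a visit timed from the last dose and not from the liver event

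*Protocol*

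**What the plan says.** Appendix 9 of the protocol has three parts: criteria a to e, the investigator's actions, and a follow-up examination.

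- **Actions.** Every effort should be made to have the patient "reassessed within 48 to 72 hours to repeat liver function chemistries and for further hepatic evaluation". After that, "Patients must be monitored 2 to 3 times per week until liver function chemistries" settle. A Liver Event Form report is due within 48 to 72 hours, and specialist advice and imaging are to be considered. The content of the further hepatic evaluation is not itemised.
- **Follow-up examination.** Here "the following assessments should be obtained at FUP and documented in the Liver Event Form". The list covers symptom course, over-the-counter and herbal products, alcohol use, risk factors for fatty liver disease, autoimmune disease, Wilson's disease, serology for six viruses and a blood count. If total bilirubin exceeds 1.5 ULN, "conjugated bilirubin should be measured", with no timing of its own.
- **FUP.** Section 2.2 states "FUP = follow-up is defined as EOT + 14 days", with a window of ± 3 days. EOT is the last day of study therapy.
- **Purpose.** Section 7.12.6.1 says: "Management and Discontinuation Criteria for Abnormal Liver Function tests have been designed to ensure patient safety and evaluate liver event etiology". It adds that "the results of further assessments and required follow-up should be recorded in the Liver Event Form", without a time point.
- **Routine schedule.** The liver-related chemistry in Table 7-1 lies within "ALP, ALT, AST, GGT, LDH, CPK, CRP, and Amylase BUN, Creatinine, TBL". Neither Table 7-1, the Section 8 visit lists nor Appendix 1 includes viral serology or conjugated bilirubin.

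**The concern.** The liver criteria exist partly to establish why a liver event happened. The specific tests for that are attached to a visit that always comes after treatment has ended, and its date depends on the last dose, not on the elevation. A site that follows the list literally would wait.

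Two things are at stake. For an elevation found while treatment continues, the investigator decides about continuation (Section 7.13) without a result that the appendix itself considers relevant. For any elevation, the work-up may be missing if the patient dies or is lost before FUP. It may also be missing if the elevation is first found at or after FUP, because no later time point is named. Section 8.5 makes EOS laboratory tests conditional and allows EOS by phone.

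**Working it through.** **Inputs.** FUP = EOT + 14 ± 3 days (Section 2.2, Table 7-2). TOC = EOT + 7 ± 2 and EOS = EOT + 28 ± 3 (Table 7-2). EA is Day 3 or 4. The planned course is 7 to 14 days and may be extended to 21 (Section 5.2). Reassessment is 48 to 72 hours, or 2 to 3 days, after the elevation (Appendix 9).

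**The plan's own figure.** Last dose to FUP: 14 − 3 = 11 and 14 + 3 = 17 days. This runs from the last dose, so it cannot be set directly against the 2 to 3 days, which run from the elevation.

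**Wait from the elevation.** Wait = (EOT day + 14) − day found, then ± 3 for the FUP window.

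| Elevation found | EOT | Nominal FUP | Wait, nominal | Wait, with FUP window |
|---|---|---|---|---|
| EA, Day 4 | Day 7 | Day 21 | 17 | 14 to 20 |
| EA, Day 3 | Day 7 | Day 21 | 18 | 15 to 21 |
| EA, Day 4 | Day 14 | Day 28 | 24 | 21 to 27 |
| EA, Day 3 | Day 14 | Day 28 | 25 | 22 to 28 |
| EA, Day 3 | Day 21 | Day 35 | 32 | 29 to 35 |
| Day 14 of an extended course | Day 21 | Day 35 | 21 | 18 to 24 |
| EOT | any | EOT + 14 | 14 | 11 to 17 |
| TOC | any | EOT + 14 | 14 − 7 = 7 | 2 to 12 |

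The TOC range uses both windows: (14 − 3) − (7 + 2) = 2 and (14 + 3) − (7 − 2) = 12. For a planned 7 to 14 day course, the EA rows give 17 to 25 days nominally and 14 to 28 with the FUP window.

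**Where an early result could affect treatment.** Scheduled chemistry is at Screening, EA, EOT, TOC and FUP, plus Day 14 if treatment is extended. Before EOT, only EA, that Day 14 visit or an unscheduled sample can reveal an elevation while dosing continues. For an elevation found at EOT or TOC, a draw 2 to 3 days later also follows the last dose.

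**Which listed items have no other named time point.** Over-the-counter and herbal use is recorded from randomization to EOS (Section 6.2.2), and over-the-counter drugs for the two weeks before randomization (Section 6.1). Height and weight are taken at Screening. Symptoms and blood counts are repeated at EA, EOT, TOC and FUP. The gap is mainly the serology and the alcohol, autoimmune and Wilson's disease history.

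**Draws already required.** If an elevation persists from EOT to FUP, 2 to 3 draws a week over a nominal 14 days gives 2 × 2 = 4 to 3 × 2 = 6 draws to which serology could be added.

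**Time to revise relatedness.** FUP to EOS: 28 − 14 = 14 days, with a minimum of (28 − 3) − (14 + 3) = 8 and a maximum of (28 + 3) − (14 − 3) = 20.

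**The case against.** The strongest reply is that early work-up is already provided for. The 48 to 72 hour reassessment covers hepatic evaluation beyond repeat chemistry, Section 7.12.1 asks that adverse events be fully investigated, and Section 7.12.7.2 adds an etiology duty for serious events, including qualifying Hy's law cases. The follow-up list can be read as a completion list, since it asks for symptom course and stop dates. The content of the Liver Event Form is not in these documents, so it may prompt for the tests early. This stands as a limit: earlier testing is allowed. It does not answer the point that the only time named for the serology is FUP.

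Four stronger readings might be inferred, and the documents do not support them:

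- **That the plan postpones the liver response until FUP.** It does not. Chemistry is followed closely from the first elevation.
- **That earlier serology would guide treatment in general.** It could do so only for elevations found on treatment. Despite the wording of Section 7.12.6.1, Appendix 9 contains no stopping rule, and no rule makes discontinuation depend on serology.
- **That relatedness cannot be judged without it.** In Section 7.12.4, excluding other causes is one of several alternative examples, not a requirement.
- **That the safety tables would be biased.** FUP precedes EOS, events still ongoing 28 days after the last dose are followed further (Section 7.12.2), and eCRF entries can be changed (Section 10.7.1).

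The risk of a missing result is also limited. Section 7.13 keeps discontinued patients in follow-up through EOS where possible.

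**Conclusion.** The point holds in a narrow form. Viral serology and part of the etiology history are named only at a visit timed from EOT. For an elevation found at EA in a 7 to 14 day course, that is 17 to 25 days later (14 to 28 with the FUP window), against 2 to 3 days for the reassessment already requested. At EOT the wait is 14 days (11 to 17). At TOC it is 7 days (2 to 12), so the gain there can be small or nil.

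The figures assume that sites read FUP as the defined visit and do not order the tests earlier on their own initiative. What remains is mainly the non-serious event under criteria a, b, d or e. The documents do not say how many patients will meet a criterion, or how many of those will miss FUP. No efficacy estimate, sample size or error rate is affected. This is a cheap improvement of the lowest severity.

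**What to change.** Reword the follow-up examination in Appendix 9 as follows:

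- Obtain the viral serology and the history items not otherwise collected (alcohol, autoimmune disease, Wilson's disease) at the 48 to 72 hour reassessment.
- Measure conjugated bilirubin when total bilirubin above 1.5 ULN is observed.
- Keep FUP for symptom course and for outstanding or repeat items.
- Apply the same event-timed rule to elevations first found at or after FUP.

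This takes one or two sentences. The tests are already requested and would only be taken sooner. The downside is a few added or unscheduled blood samples, mostly at draws that Appendix 9 already asks for.

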#### History of Statistical Analysis Plan Amendments

Version 1 (Original)	13 Jul 2017
Version 2	24 Jul 2018
Version 3	27 Jun 2019
Revisions to Version 1 and 2 are documented in Version 3	

## RECORDS ON REVISIONS

Version	Date for creation or modification	Person in charge	Remarks
Ver 1.0	13 Jul 2017	[REDACTED]	Originally prepared
Ver 2.0	24 Jul 2018	[REDACTED]	

▪ Update per Clinical Study Protocol Version 4

▪ Update objective of this study

▪ Specify time point for vital sign (Section 10.3)

▪ Delete section ECG analysis (Section 10.4)

▪ Add description for subjects with Stenotrophomonas maltophilia will be included in CR MITT population (Section 5.3)

▪ Update criteria for eradication for cUTI subject (section 9.1)

▪ Add description for DSMB

▪ Specify using corrected APACHE II score 9.3.2.2

▪ Add the rule of analysis visit and baseline definition (Sections 6.3 and 6.5)

▪ Add logic for missing time (Section 6.4.1)

▪ Add data handling if reported bacteria name is different between local and central (Section 6.7.1)

▪ Add definition of additional antibiotics (Section 6.8)

▪ Add definition of study drug regimen and add subgroup analysis using it (Sections 6.9, 9.4.1.1, and 9.4.1.2)

▪ Add analysis for new infection (Section 9.4.1.2)

▪ Add analysis regarding susceptibility (Section 7.2)

▪ Add sensitivity clinical and microbiological outcome (Section 9.2)

▪ Add indeterminate at TOC carried forward

			
to FU (Sections 9.1.2 and 9.1.4)
 

▪ Add subgroup analysis for type of CR baseline pathogen, region and APACHE II (Section 9.3.3)

▪ Add analysis for HABP/VABP/HCABP + BSI/sepsis (Section 9.4.1)

▪ Add analysis for cUTI for mortality (Section 9.4.1)

▪ Clarify using standard unit for laboratory data analysis (Section 10.2)

▪ Specify decimal space for PK analysis (Section 14)

▪ Change decimal space for standard deviation and error. (section 14)

2.1	15 Aug 2018	[REDACTED]	

▪ Clarify analysis for baseline pathogen (section 7.2)

▪ Add decimal space for calculated value. (section 14)

▪ Add calculation formula for appendix 2.

2.2	03 Dec 2018	[REDACTED]	

▪ Change the wording from sensitivity to supplementary per ICH E9 R1

▪ Clarify the interim analysis for DSMB

▪ Exclude neomycin oral administration from additional antibiotics (section 6.8).

▪ Clarify Composite of Survival and No Change in Antibiotic Treatment will be determined by Shinogi internally rather than EDC data (section 9.4.1.9).

▪ Exclude PTT from LAB analysis (section 10.2)

▪ Minor update of wording

2.3	12 Feb 2019	[REDACTED]	

▪ Specify medical monitor will adjudicate additional antibiotics based on available data, and delete sentences about neomycin oral administration.

2.4	11 Apr 2019	[REDACTED]	

▪ Delete signature page to use Veeva Vault eSignature due to change TMF management plan.

▪ Terminology change from microbiological

			
eradication/failure to eradication/persistence. (Section 9.1.6, 9.1.7, 9.2.6)
 

▪ Change terminology from protocol deviation list to protocol deviation specification. Also clarify criteria for ME population is specified in the document. (section 5.4 and 8.1)

▪ Change the definition of new/super infection to new pathogen on or after Day 3 by the input from medical group. (section 9.1.5)

3.0	27 Jun 2019	[REDACTED]	

▪ Add time imputation for lab data and microbiological data if time is missing (section 6.4.1 and 6.4.2)

▪ Add CR MITT 2 Population (section 5.3.1) and analysis using CR MITT2 (section 7.1, 9.4.1.1 and 9.4.1.2)

▪ Add data handling for subject who receive cefiderocol after BAT completion (section 5.5 and 10.1.1)

▪ Add analysis window for premature EOT

▪ Differentiate persistence and recurrence which was originally counted together (section 9.1.6) and update table 9-3

▪ Add overall mortality until EOS. In addition, add overall mortality including death after EOS. (section 9.4.1.6)

▪ Add analysis for fatal AE (section 10.1)

▪ Clarify if investigator consider BSI subject as clinically cured and no need to collect blood sample, considered as presumed eradication (section 9.1.3.3 and 9.1.4.3)

## LIST OF ABBREVIATIONS AND DEFINITIONS OF TERMS

ADR	adverse drug reaction
AE	adverse event
ALT	alanine aminotransferase
APACHE II	Acute Physiology and Chronic Health Evaluation II
AST	aspartate aminotransferase
ATC	Anatomical Therapeutic Chemical
BAL	bronchoalveolar lavage
BAT	best available therapy
BMI	body mass index
BSI	bloodstream infections
CFUs	colony-forming units
CI	confidence interval
CLSI	Clinical and Laboratory Standards Institute
CR-ME	Carbapenem-resistant Microbiologically Evaluable Population
CR Micro-ITT	Carbapenem-resistant Microbiological Intent-to-treat Population
CrCl	creatinine clearance
cUTI	complicated urinary tract infection
DSMB	data safety monitoring board
EA	Early Assessment
ECG	electrocardiogram
eCRF	electronic case report form
eGFR	estimated glomerular filtration rate
EMA	European Medicines Agency
EOS	End of Study
EOT	End of Treatment
EUCAST	European Committee on Antimicrobial Susceptibility Testing
FiO 2	fraction of inspired oxygen
FU	Follow-up
HABP	hospital-acquired bacterial pneumonia
HCABP	healthcare-associated bacterial pneumonia
IMP	investigational medicinal product
ITT	intent-to-treat
IWRS/IVRS	interactive web or voice response system
MDRD	modification of diet in renal disease
MedDRA	Medical Dictionary for Regulatory Activities

---

MIC	minimum inhibitory concentration
Micro-ITT	Microbiological Intent-to-treat Population
mITT	modified intent-to-treat
$\%T_{f>MIC}$	percentage of the dosing interval for free-drug plasma concentration to be above the minimum inhibitory concentration
PaO 2	partial pressure of arterial oxygen
PK	pharmacokinetics
PSB	protected specimen brush
PT-INR	prothrombin time-international normalized ratio
SAE	serious adverse event
SAP	statistical analysis plan
SD	standard deviation
SIRS	systemic inflammatory response syndrome
SOC	System Organ Class
SOFA	Sequential Organ Failure Assessment
TIBC	total iron-binding capacity
TOC	Test of Cure
ULN	upper limit of normal
VABP	ventilator-associated bacterial pneumonia
WBC	white blood cell (count)
WHO	World Health Organization

## 1. INTRODUCTION

This Statistical Analysis Plan (SAP) presents details, including methods of analyses, of the efficacy and safety analyses described in [Section 9: “PLANNED STATISTICAL METHODS”](#) of the protocol (Protocol No. 1424R2131: Version 4 dated 16 Nov 2017). Details of outputs (or mock-ups of tables, figures, and listings) from analyses in this SAP, will be included in a separate document (“Tables, Figures, and Listings Shells”) prepared separately. Any deviations from this analysis plan will be substantiated by sound statistical rationale and will be documented in the final clinical study report.

## 2. STUDY OVERVIEW

This is a Phase 3, multicenter (multinational), open-label, parallel-group, randomized, active-controlled study in approximately 150 subjects with documented carbapenem-resistant Gram-negative bacterial infections. Subjects meeting eligibility criteria and assessed by the investigator to require 7 to 14 days of intravenous treatment in hospital will be randomized (2:1) to either cefiderocol 2 g received intravenously over 3 hours, every 8 hours, or best available therapy (BAT).

The treatment duration for cefiderocol or BAT is anticipated to be 7 to 14 days, which are consistent with published treatment guidelines for serious infections. Based on the investigator’s clinical assessment of the subject, treatment may be extended up to 21 days.

## 3. STUDY OBJECTIVES

### 3.1 Primary Objective

- To assess, at Test of Cure (TOC), the clinical outcome to therapy with cefiderocol or BAT in adult subjects with either hospital-acquired bacterial pneumonia (HABP)/ventilator-associated bacterial pneumonia (VABP)/healthcare-associated bacterial pneumonia (HCABP) or bloodstream infections/sepsis (BSI/sepsis) caused by carbapenem-resistant Gram-negative pathogens
- To assess, at TOC, the microbiological outcome to therapy with cefiderocol or BAT in adult subjects with complicated urinary tract infection (cUTI) caused by carbapenem-resistant Gram-negative pathogens

### 3.2 Secondary Objectives

- To assess the safety of cefiderocol
- To assess the clinical outcome of treatment with cefiderocol or BAT in subjects with either HAP/VABP/HCABP or BSI/sepsis at End of Treatment (EOT) and Follow-up (FU)
- To assess the clinical outcome of treatment with cefiderocol or BAT in subjects with cUTI at EOT, TOC, and FU

- To assess the microbiological outcome of treatment with cefiderocol or BAT in subjects with either HABP/VABP/HCABP or BSI/sepsis at EOT, TOC, and FU
- To assess the microbiological outcome of treatment with cefiderocol or BAT in subjects with cUTI at EOT and FU
- To assess the microbiological outcome of treatment with cefiderocol or BAT in subjects with bacteremia (regardless of the primary infection diagnosis) at EOT, TOC, and FU
- To assess the composite clinical and microbiological outcome of treatment with cefiderocol or BAT in subjects with cUTI at EOT, TOC, and FU
- To assess the all-cause mortality at Day 14 and Day 28 in subjects with HABP/VABP/HCABP and BSI/sepsis
- To compare cefiderocol with BAT in subjects with HABP/VABP/HCABP, cUTI, or BSI/sepsis based on the composite endpoint of survival and no change in antibiotic treatment due to either lack of therapeutic benefit or drug-related toxicity at TOC

 TOC is defined as End of Treatment (EOT) + 7 days ( $\pm$  2 days).

 BSI/sepsis is a group of patients with documented carbapenem-resistant Gram-negative infections in the bloodstream (BSI) or in a body site other than the urinary tract (cUTI) or lung (HABP/VABP/HCABP) and in case of sepsis, evidence of systemic inflammatory response syndrome (SIRS) is required.

 EOT = End of Treatment is defined as the last day of study therapy.

 FU = Follow-up is defined as EOT + 14 days ( $\pm$  3 days).

